Neuroimaging of Tryptophan Challenge in People with Schizophrenia and Healthy Controls

March 28, 2016

NCT02067975

Neuroimaging of Tryptophan Challenge in People with Schizophrenia and Healthy Controls

PI: [name] , M.D.

Co-Investigators: [name].

[name].

[name].

[name].

Overview of Research Design:

The study will be a double-blind, placebo-controlled, cross-over, tryptophan (TRYP) challenge study to examine the effects of increased kynurenic acid (KYNA) on neuropsychological test performance; patterns of fMRI activation and connectivity during the performance of a relational memory task; and ¹H-MRS measures of medial prefrontal cortex (mPFC) glutamate. The effects of increased KYNA on fMRI default network activity and peripheral markers of the kynurenic pathway, HPA axis, and inflammatory system will also be explored. Participants will include people with DSM-5/DSM-IV-TR schizophrenia or schizoaffective disorder (SRDs) and healthy controls. The healthy control group will be used to estimate the normal response parameters to the TRYP challenge. Participants will be randomly assigned to either TRYP (6 grams) or placebo. They will take the study medication 120 min prior to MRI scanning. TRYP administration will be used to increase peripheral kynurenic acid levels, which will lead to increased CNS production of KYNA.

Primary Aims:

- 1) To determine if TRYP-induced elevated KYNA levels impair performance on neuropsychological measures of attention, processing speed verbal and visual memory, and working memory.
- 2) To determine if TRYP-induced elevated KYNA levels alter neural circuit activation and connectivity between the dorsolateral prefrontal cortex (DLPFC) and hippocampus (HPC) during the performance of the Relational and Item-Specific Encoding (RISE; 90) task.
- 3) To determine if TRYP-induced elevated KYNA levels alter glutamate levels in the medial (mPFC), a brain region hypothesized to be important in the performance of cognitive tests.

Secondary Aims:

- 1) To examine if TRYP-induced elevated KYNA levels alter resting patterns of default network activation and connectivity.
- 2) To examine if baseline and/or post-challenge HPA axis and inflammatory indices moderate or mediate the response of behavioral or functional measures to TRYP-induced elevated KYNA levels.

Inclusion/Exclusion Criteria:

Inclusion Criteria (Participants with Schizophrenia)

- 1) Males and females between the ages of 18 and 55 years

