WMS®-III Spatial Span: uses a board on which 10 cubes are irregularly spaced, and the respondent taps cubes in the same (or reverse) sequence as the test administrator; the total score will be used to assess nonverbal working memory.

Laboratory Assessments: The following laboratory assessments will be collected:

Kynurenone, KYNA, and 3-HK: After thawing, serum (100 µl) will be acidified with 50 µl of 6% perchloric acid and centrifuged in a microfuge (10 min). The kynurenone pathway metabolites will be determined in the supernatant (20 µl) using high performance liquid chromatography (HPLC) methods.

Cytokine Profile: The immune panel consists of 12 cytokines: interferon- γ , IL-1 β , IL-1RA, IL-2, IL-4, IL-6, IL-10, IL-12, IL-13, CXCL8, GMCSF, and TNF- α . These cytokines are part of the Type 1 and Type 2 immune responses, have been previously implicated in schizophrenia (102-105), and have been linked to changes in KYNA levels (106-109). The cytokine samples will be collected in tubes containing EDTA, immediately cooled on and centrifuged under refrigeration and stored at -80°C until analyzed. The cytokines will be analyzed by the University of Maryland Cytokine Core Laboratory using either Multiplex Luminex technology or ELISA.

Cortisol and ACTH: The neuroendocrine blood samples will be collected in EDTA-containing tubes, immediately placed on ice, centrifuged under refrigeration and stored at -80°C until analyzed by LabCorp®. To reduce the possible effect of stress on cortisol levels, participants will remain in the same room in a calm environment. To control for menstrual effects, challenge studies for females will occur in the first half of the menstrual cycle. If women are oligomenorrheic, they will be enrolled between 1-14 days of their last menstrual period, and amenorrheic women will be enrolled without regards to hormonal status.

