Analysis Plan: For exploratory analysis of changes in neural activation and functional connectivity in the default mode network (i.e., medial temporal lobe, mPFC, posterior cingulate cortex, ventral precuneus and medial, lateral and inferior parietal cortex) in healthy controls and participants with SRDs given TRYP or placebo, we will use models similar to those outlined for Specific Aim 2.

2): To examine if baseline and/or post-challenge HPA axis and inflammatory indices moderate or mediate the response of behavioral or functional measures to TRYP-induced elevated KYNA levels.

Analysis Plan: We will conduct exploratory analyses at unadjusted two-sided alpha = 0.05. People with SRD have been reported to have higher brain KYNA levels than healthy controls, and have major differences in behavioral and functional measures. Accordingly, we will analyze mediating and moderating effects of KYNA separately in the two groups, following the approach of Kraemer et al (118). To test moderation, we will examine the repeated measures models: change (Post-TRYP - Pre-TRYP) in behavioral outcome = treatment + pre-TRYP KYNA on test day + treatment x pre-TRYP KYNA, where the treatment x pre-TRYP KYNA on test day measures the change of slope for pre-treatment KYNA in predicting change in behavioral outcome. If this difference in slopes = 0, there is no mediator effect for pre-TRYP KYNA. Similarly, to assess mediation, we will fit a similar model to assess the difference between treatments (TRYP versus placebo) in slopes predicting change in the behavioral response from change in KYNA to whether change in KYNA mediates the treatment effect, noting that this is not the same as assessing causality (123).

Risks to Human Subjects

a. Human Subject Involvement, Characteristics and Design. The proposed project meets the definition of a “Clinical Trial.” This challenge study will enroll both healthy controls and people with schizophrenia. Following a period of baseline evaluation and assessment, participants (healthy controls and schizophrenia patients) will randomly participate in two visits. On one of the two visits, the participant will receive L-tryptophan (TRYP), and on the other visit the participant will receive placebo as an oral slurry. At each of the two visits, all participants will undergo morning baseline assessments followed by medication dosing, assessments and imaging procedures.

Potential Risks to Human Subjects:

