All records of the research will be kept in locked files with subjects identified by code only. A separate file will hold the code key. Subjects will not be personally identified in any publications or reports of the study. All biological specimens collected for research purposes will be identified at the laboratory by code only. Whenever possible, existing clinical laboratory data will be used as a source of information for the study, which will minimize testing done on subjects. Any data used will be recopied to research files with the subject identified by code only. Computerized records of data are kept in password-protected computers in locked rooms. Appropriate firewalls and protections of computerized data are maintained to ensure that entry by those other than research personnel is not possible.

Potential Benefits of the Proposed Research to the Participants and Others There are few potential benefits to participating in the study. Participants will have a series of medical and laboratory workup prior to study start that may provide new or helpful information on their physical and mental health. Mild and transient changes in neurocognition are possible or even expected. We feel the importance of the knowledge gained outweighs the risks of the study.

Importance of the Knowledge to be Gained:

We will be able to examine, for the first time, the connection between the kynurene pathway, cognitive function and neuroimaging in people with schizophrenia. In addition, we will examine the role of stress hormones and immune function in the control of kynurene pathway metabolism. This important information could be the first clinical study to link this pathway to symptoms and outcomes of people with schizophrenia.

Data and Safety Monitoring Plan:

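### Secondary Aim 2 asks about HPA-axis and inflammatory indices, but only KYNA models are written, and the slope difference named for mediation is zero when the mediator slope is the same on both days

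*Combined protocol and SAP*

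**What the plan says.** In the Statistical Analysis section, Secondary Aim 2 is: "To examine if baseline and/or post-challenge HPA axis and inflammatory indices moderate or mediate the response of behavioral or functional measures" to TRYP-induced KYNA elevation. The analysis plan directly below it states "we will analyze mediating and moderating effects of KYNA separately in the two groups" and writes two models.

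- **Moderation.** Within-visit change in a behavioral outcome is modeled on treatment, pre-dose KYNA that day, and their product. The stated reading is "If this difference in slopes = 0, there is no mediator effect for pre-TRYP KYNA".
- **Mediation.** The plan is "to assess mediation, we will fit a similar model to assess the difference between treatments (TRYP versus placebo) in slopes" of behavioral change on change in KYNA.

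On error control it says "We will conduct exploratory analyses at unadjusted two-sided alpha = 0.05". The moderator/mediator approach is cited as reference 118.

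Elsewhere, the Overview of Research Design says that effects on "peripheral markers of the kynurenic pathway, HPA axis, and inflammatory system will also be explored", and Importance of the Knowledge to be Gained says "we will examine the role of stress hormones and immune function in the control of kynurene pathway metabolism". Under Laboratory Assessments, "The immune panel consists of 12 cytokines", and cortisol and ACTH are also measured. The Assessment Schedule places the draws at baseline, at 30, 60 and 90 minutes after ingestion, and at the second cognitive battery. Imaging takes place once per visit, after dosing.

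**The concern.** There are three gaps.

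1. The variables in the aim are not the variables in the models. If the HPA and inflammatory indices are analyzed at all, the choice of index, post-dose time and outcome could be made after the data are seen.
2. A difference in slopes is an interaction. Mediation needs treatment to move the mediator and the mediator to predict the outcome. A test of the interaction alone addresses neither, so it can mislead in both directions.
3. The aim includes functional measures, but the written model needs a post-minus-pre change. With a single post-dose scan per visit, no such change exists for imaging.

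There are also two editorial slips. The sentence that concludes the moderation test speaks of a mediator effect. And reference 118 is a review of tryptophan loading; the paper on mediators and moderators is reference 123.

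**Working it through.** The documents give no power or sample-size figure for this aim, so there is none to reproduce.

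**Step 1: aim against models**

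| Element of the aim | What the plan writes |
|---|---|
| HPA indices (cortisol, ACTH) | no term in any model |
| Inflammatory indices (12 cytokines) | no term in any model |
| Baseline and/or post-challenge values | pre-dose KYNA; change in KYNA with no post-dose time named |
| Behavioral measures | change-score model, KYNA only |
| Functional measures | no model under this aim |

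**Step 2: algebra**

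Let T = 1 for TRYP and 0 for placebo, M = change in KYNA, Y = change in outcome, with intercepts omitted:

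- M = aT + e′
- Y = c′T + bM + dTM + e

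The slope is b on placebo and b + d on TRYP, so the quantity that the plan names is d.

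- If d = 0, the mediated effect is a × b, which need not be zero.
- If a = 0, the mediated effect is zero whichever slope is used (a × b or a × (b + d)), while d can take any value.

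This needs no assumed inputs.

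**Step 3: size, by simulation**

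From the protocol: 50 × (1 − 0.10) = 45 completers per group, two visits, two-sided 0.05. Everything else is assumed, because the documents give no KYNA SD, slope or within-person correlation. The first set of assumptions is:

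- within-person correlation 0.3-0.6;
- slopes in outcome SD per SD of KYNA change on TRYP;
- 4,000 datasets in each of 20 scenarios;
- random-participant model fitted by REML.

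The comparison is a two-part rule: a paired t-test of TRYP on change in KYNA, and a 2-df joint test of the KYNA main effect and interaction, both with p < 0.05.

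| Case | Slope on TRYP | Slope-difference test rejects | Two-part rule met |
|---|---|---|---|
| (a) Full mediation, common slope, KYNA up 3 SD, placebo/TRYP SD ratio 0.1-1.0 | −0.3 | 4.6-5.4% (both slopes) | 43.1-85.8% |
| (a) same | −0.5 | 4.6-5.4% (both slopes) | 85.5-99.9% |
| (b) TRYP does not change KYNA, placebo slope 0, SD ratio 0.5-1.0 | −0.3 | 14.5-40.7% | 1.8-4.8% (both slopes) |
| (b) same | −0.5 | 32.8-81.0% | 1.8-4.8% (both slopes) |

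A participant-bootstrap interval for the indirect effect was then also required (correlation 0.5; 200 datasets × 300 resamples). The full criterion was met in 53% (slope −0.3) and 95% (slope −0.5) of case (a) at SD ratio 0.5, and in 1.0-2.5% of case (b) at slope −0.5.

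A second set of assumptions used a KYNA rise of 2 SD, KYNA-change SD 1.0 on TRYP and 0.3 on placebo, participant SD 0.5, residual SD 1.0 and 2,000 datasets. For common slopes of −0.25, −0.5 and −0.8:

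- the slope-difference test rejected 6.4%, 4.8% and 5.0%;
- a joint test of TRYP on KYNA and the common slope rejected 36%, 86% and 99.8%.

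With n = 2,000 and slope −0.5 (300 datasets) the figures were 3.7% and 100%, so a larger sample does not help. With TRYP not changing KYNA, equal SDs and slopes of 0 and −1, they were 98% and 4.5%.

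**Step 4: number of tests**

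There are 12 cytokines + cortisol + ACTH = 14 indices. With two roles, six cognitive tests and two groups:

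- all indices: 14 × 2 × 6 × 2 = 336 tests; 336 × 0.05 = 16.8 false positives expected if all nulls hold;
- three indices: 3 × 2 × 6 × 2 = 72; 72 × 0.05 = 3.6;
- KYNA as now written: 1 × 2 × 6 × 2 = 24; 24 × 0.05 = 1.2.

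**The case against.** The plan says it follows a published moderator/mediator approach, which may itself require a treatment effect on the mediator or a mediator main effect. The similar model would probably contain that main effect. This cannot be checked from the documents, and it is a fair limit. But the plan writes out its own criterion, which is the slope difference, and does not say that either of the other terms will be tested.

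The false-positive case is remote for KYNA, since the design expects TRYP to raise it. That largely stands, although the pilot result reported is a rise in kynurenine, in ten healthy controls. The false-positive direction matters most if the same criterion is carried over to cortisol, ACTH or cytokines, where the documents give no TRYP effect to rely on.

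The simulation inputs are assumed, and a rejection rate near 5% merely restates that the slopes are equal. Both are true; the figures illustrate the algebra. The two-part rule also cannot separate mediation from a shared cause of KYNA change and outcome change. That stands too, and the plan already says that its mediation analysis does not establish causality.

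Three smaller points also stand. The test counts omit functional outcomes, so they understate the total. A cytokine composite is a suggestion without support in the documents, since the panel spans two types of immune response. The statements in the Overview and in the section on knowledge to be gained concern related questions, not moderation or mediation of behavior; they show that these markers matter to the study, and they have no model either.

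**Conclusion.** The concern holds. The mismatch between aim and models is read directly from the text, and the behavior of the slope difference is algebra; neither rests on an assumed value. Under common-slope mediation the named test rejects at about its alpha at any sample size. When TRYP does not move the mediator but the slopes differ, it rejected in 14.5-81.0% of datasets over the first set of assumptions. Those percentages are illustrative and would change with the true KYNA SDs, slopes and within-person correlation.

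The consequence is limited: this is a secondary, exploratory analysis, and the primary-aim models are unaffected. But exploratory status does not explain why the models use a different variable from the aim. The plan should be changed.

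**What to change.** Revise the Secondary Aim 2 analysis plan as follows.

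- Name a short set of indices, for example cortisol, ACTH and one cytokine composite or another choice the investigators can justify. Put them in the moderator and mediator models, and state the sampling time or summary used for each, including for change in KYNA.
- For mediation by KYNA or any index, require a TRYP effect on the mediator plus a main effect or treatment interaction of the mediator in the outcome model.
- Report the indirect effect with a bootstrap interval that resamples participants. State how it is computed when the interaction is kept, for example a × b and a × (b + d) separately.
- For functional outcomes, state a model with the post-dose value at each visit as the response.
- Apply the FDR method of Primary Aim 1 across this set, or keep 0.05 unadjusted. In either case label the results hypothesis-generating.
- Change mediator to moderator in the sentence that concludes the moderation test, and correct citation 118 to 123.

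The cost is SAP wording and extra analysis of samples already scheduled, with no new visits. The downside is more exploratory tests: three indices add 72 on the six cognitive tests to the 24 for KYNA, and functional outcomes add more. That is the reason for a short set or FDR control.

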Assessment Schedule: The clinical assessments will be administered prior to administration of the study medication, immediately prior to the MRI scan, upon completion of the MRI scan, and at the follow-up safety assessment, which will be conducted 75 min after the completion of the MRI scanning. The cognitive assessments will be conducted prior to the administration of the study medication and after the MRI scanning is completed and the participant has had lunch. The laboratory assessments will be collected at pre-TRYP challenge baseline, and 30 min, 60 min and 90 min post ingestion. The final laboratory assessment will be collected at the time of the second administration of the cognitive battery. The safety assessments will be administered

prior to administration of the study medication, every 30 min after medication administration, upon completion of the MRI scan, and at the follow-up safety assessment.

Table 1. Assessment Schedule.

	Study Lead In (up to 2 weeks)	Challenge Visit: Estimated Time of Assessment	Challenge Visit: Actual Time of Assessment	Initials
Informed Consent, ESC	X			
SCID and diagnostic interview, MRI screening	X			
Medical Screening Medical Hx, physical exam, blood draw, urinalysis, toxicology screen, pregnancy test (females), EKG, medication use screening, caffeine use screening, Birth Control Selection (females)	X			
Clinical Stability Determination (schizophrenia group only seen on two visits, healthy controls one visit) 2 unchanged CGIs	X			
Mock scanning session	X			
Scheduling of 2 challenge visits and NPO order for 12 hours in advance of admission on challenge study days	X			
Participant Admission/BSU Arrival Review of Study Procedures and retrospective recall of food intake (past 12 hours). Collect personal items not safe during MRI testing.		7:30 am		
Urine pregnancy (females), expired CO, urine toxicology and blood alcohol testing, MRI screening		7:45 am		
Insertion of indwelling IV line, fluids, period of relaxation		8:00 am		
Laboratory Assessments (1): cortisol, ACTH, kynurenine, KYNA, 3-HK, cytokines		8:15 am		
Cognitive Measures (1): HVLT-R, BACS Symbol Coding, BVMT, CPT-IP, WMS®-		8:30 am		

III, LNS				
Vital signs, SEC, SSS Clinical Assessments (1): BPRS, SANS, CDS, CGI		9:15 am		
Oral Administration of Medication (Tryptophan 6 gram/ Placebo)		10:00 am		
Protein Free Snack		10:15		
Vital signs, SEC, SSS Laboratory Assessments (2)		10:30		
Vital signs, SEC, SSS Laboratory Assessments (3)		11:00 am		

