Double-Blind Challenge Phase: The Double-Blind Challenge Phase will utilize a placebo-controlled, cross-over design. Participants who continue to fulfill entry criteria will be entered into the Double-blind Challenge Phase. There will be two Challenge Phase visits. On the day of each visit, the participants will arrive at the Brief Stay Unit (BSU) at 7:30AM; all participants will have fasted since midnight. At the BSU, an indwelling I.V. will be inserted for the repeated laboratory assessments and the initial clinical, cognitive, laboratory, and safety assessments (including urine pregnancy test for female participants) will be completed. Upon completion of the initial assessments, participants will receive the challenge medication. Participants will be randomly assigned to receive TRYP (6 grams) or placebo. They will receive the other study medication on the second visit (i.e., placebo or TRYP). The 6 gram dose was chosen based on previous work showing cognitive effects to be associated with doses above 5 grams (118) and our pilot work, in which we have demonstrated that, in ten healthy controls TRYP (6 grams) produces a robust increase in kynurenone. TRYP and placebo will be administered in oral slurry. A non-blind pharmacist will dispense all study medications. The blind will be broken only if a medical emergency requires this information. If this occurs, the participant will be withdrawn from the study. Two hours after ingestion of TRYP or placebo, participants will be transferred to the CBIR, which is in a building adjacent to the BSU, where they will undergo the following MRI assessments: 1) spectroscopy for the assessment of glutamate, 2) fMRI resting scan; and 3) fMRI during relational and item memory tasks. We chose to begin scanning 120 min after study medication ingestion, because our preliminary data suggests that serum kynurenone initially becomes elevated 30 min after TRYP ingestion, but continues to increase over the next three hours; we wanted to ensure sufficient time for kynurenone to cross the BBB and be converted to KYNA. Kynurenone levels will remain elevated for at least 3.5 hours, which is sufficient time to complete the MRI assessments and post-imaging cognitive assessments. The cognitive assessments will be conducted prior to the administration of the study medication and after the MRI scanning is completed. The post-baseline clinical, laboratory, and safety assessments will be conducted as described above.

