Statistical Analysis: Initially, we will examine responses to TRYP or placebo challenge separately in healthy controls and participants with schizophrenia-related disorders (SRD), anticipating that different basal states of KYNA metabolism may result in distinct responses to TRYP challenge in the two groups. Secondary analyses will compare responses to TRYP challenge in the two groups.

Primary Aims:

- 1): To determine if TRYP-induced elevated KYNA levels impair performance on neuropsychological measures of attention, processing speed verbal and visual memory, and working memory.

Analysis plan: To facilitate comparison of the magnitude of effects across the six cognitive tests from the MCCB, we will utilize the MCCB T-scores for each test. For each cognitive measure, we will fit a mixed model for repeated measures ANCOVA: post-study drug score on i-th day = pre-study drug score on i-th day + treatment on i-th day + day + treatment x day, where day (=1,2) is an indicator of whether the scores were collected on the first or second day of testing. In this model, the treatment effect estimates the average TRYP - placebo difference across the two possible orders of testing, and the treatment x day effect estimates how much this difference might depend on whether TRYP or placebo was administered first. Learning effects from repeated cognitive testing could produce diminishing increases across the four repeated administrations of each test, resulting in larger pre-post differences in scores on the first versus second day of testing; these learning effects could be different following dosing with TRYP versus placebo, masking the existence of treatment x day interactions. Since the MCCB tests were chosen to have small learning effects ($d < 0.1$; 101), we anticipate these learning effects and possible interactions with treatment will be small. To take account of multiple testing with six cognitive tests, we will use the Benjamini-Hochberg False Discovery Rate (FDR; 120) modification of the Bonferroni method: we will compare the six p-values from largest to smallest to successively stricter critical values $c_j = 0.05 \times (6-j+1)/6$; if the j-th p-value is less than c_j , we will reject that null hypothesis and all null hypotheses corresponding to smaller p-values. To compare the magnitude of T-score differences between TRYP and placebo among cognitive tests, we will add terms for cognitive test and test x treatment interactions to the model described above.

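### The exploratory Secondary Aim 2 moderation model analyses raw change without the pre-dose score or day, giving up precision whose size depends on an unreported correlation

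*Combined protocol and SAP*

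**What the plan says.** Under Statistical Analysis, Secondary Aim 2, the moderation model is "change (Post-TRYP - Pre-TRYP) in behavioral outcome = treatment + pre-TRYP KYNA on test day + treatment x pre-TRYP KYNA". It is fitted separately in each group. The mediation model is described as similar and compares treatments on "slopes predicting change in the behavioral response from change in KYNA". Neither has a pre-dose behavioural score as covariate, and neither has a day or order term. The section opens with "We will conduct exploratory analyses at unadjusted two-sided alpha = 0.05".

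Under Primary Aim 1, each cognitive test is modelled as "post-study drug score on i-th day = pre-study drug score on i-th day + treatment on i-th day + day + treatment x day". The models for Primary Aims 2 and 3 carry order terms. The Aim 1 text says that learning effects could diminish over the four administrations, "resulting in larger pre-post differences in scores on the first versus second day of testing". It then says that the tests were chosen to have small learning effects (d < 0.1) and that these effects are expected to be small.

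The study is a "placebo-controlled, cross-over design" with two challenge visits (Double-Blind Challenge Phase). On each visit, "The cognitive assessments will be conducted prior to the administration of the study medication and after the MRI scanning is completed", so a same-day pre-dose score exists for every cognitive test.

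**The concern.** In a cross-over, a person's stable ability cancels when the two days are compared. What remains of the pre-dose score is its day-to-day variation. Part of that is a genuine day effect shared with the post-dose score, and the rest is test error. A change score subtracts all of it with a coefficient of 1. If the shared part is small, the subtraction adds noise instead of removing it. A model that estimates the coefficient avoids this, and Aim 1 already moves in that direction for the cognitive tests.

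Precision matters here because Secondary Aim 2 holds the only written models that relate behaviour to measured KYNA. The primary-aim models contain treatment but no KYNA term. The moderation test is an interaction, fitted within groups of about 45 completers, where power is limited to begin with.

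**Working it through.** **The plan's own figure.** Under Recruitment, 50 are enrolled per group with 10% attrition: 50 × 0.9 = 45 completers, as stated. The documents give no standard deviation, pre-post correlation, between-day correlation or power for the cognitive outcomes. The only test-retest figures are for spectroscopy (intra-class correlations of 0.82 and 0.89), not cognition. Every correlation below is therefore an assumption.

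**Closed form.** Let v be the within-person variance of a score, and r the within-person correlation of pre- and post-dose scores on the same day. For the TRYP-day minus placebo-day difference:

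- raw change: variance = 4v(1 − r)
- post-dose score with a free within-person pre-dose slope: variance = 2v(1 − r²)
- ratio of the second to the first = (1 + r)/2, so the standard error under raw change is √(2/(1 + r)) times the other.

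The simulated column gives ratios for the moderation slope with 45 people, day shifts of 0.05 to 0.1 SD and a free within-person slope. The last column is 45 × (1 + r)/2.

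| Assumed r | √(2/(1 + r)) | Simulated ratio | Completers' worth of information kept by raw change |
|---|---|---|---|
| 0 | 1.414 | 1.36 to 1.41 | 22.5 |
| 0.25 | 1.265 | 1.23 to 1.24 | 28.1 |
| 0.5 | 1.155 | 1.10 to 1.16 | 33.8 |
| 0.7 | 1.085 | 1.05 to 1.07 | 38.3 |
| 0.9 | 1.026 | 1.00 to 1.02 | 42.8 |

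**Which correlation counts.** It is the within-person one: r = (same-day correlation − between-day correlation)/(1 − between-day correlation). A high raw correlation does not by itself remove the loss. With 0.85 same-day and 0.70 between-day, r = 0.15/0.30 = 0.5. To reach r = 0.9 with 0.70 between-day, the same-day correlation must be 0.70 + 0.9 × 0.30 = 0.97.

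**Copying Aim 1's term versus splitting it.** A single pre-dose coefficient has to serve both between-person and within-person variation, so it settles on a compromise. A second simulation used 45 people, two days, balanced order, a random-intercept REML fit, a day shift of 0.05 SD, a KYNA intra-class correlation of 0.8 and 600 runs per setting. It gave these ratios of the model standard error for treatment by KYNA (planned change model over alternative):

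| Between-day / same-day correlation | r | Alternative: Aim 1's single term plus day | Alternative: split term plus day |
|---|---|---|---|
| 0.6 / 0.6 | 0 | 1.197 | 1.339 |
| 0.7 / 0.7 | 0 | 1.151 | 1.364 |
| 0.8 / 0.8 | 0 | 1.089 | 1.349 |
| 0.7 / 0.8 | 0.33 | 1.083 | 1.179 |
| 0.7 / 0.85 | 0.5 | 1.051 | 1.115 |
| 0.8 / 0.95 | 0.75 | 1.015 | 1.048 |

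Copying Aim 1's form therefore recovers about 1.5% to 20%. The split recovers about 5% to 36% over the same settings.

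**The day term alone.** Omitting a day shift δ (in SD units) multiplies the standard error of the treatment contrast by √[(4(1 − s) + δ²)/(4(1 − s))], with s the same-day correlation. At δ = 0.1:

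- s = 0.7: √(1.21/1.20) = 1.004
- s = 0.9: √(0.41/0.40) = 1.012

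At a shift of 0.05 SD, adding day alone left the simulated interaction standard error within about 1%, with no gain.

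**The case against.** The analyses are labelled exploratory, and change scores are conventional and easy to read. Order is randomised in balanced blocks, so leaving out the pre-dose score and day does not bias the moderation interaction. All of that stands, and it limits the point to precision.

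Several stronger readings are tempting but not supported:

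- A reader might take a penalty of 15% to 41% as established. That range is simply the formula for r from 0.5 down to 0. Nothing in the documents places r there, and at 0.7 to 0.9 the same formula gives 8.5% to 2.6%.
- A reader might treat the whole loss as the gap between the Aim 1 and Secondary Aim 2 models. The larger figures need a free within-person slope, which Aim 1's single pre-dose term does not provide.
- A reader might infer that the plan predicts larger change on day 1. It says only that learning could produce this, and it expects the effect to be small. Omitting day would matter only if the shift were well above d = 0.1. At 0.5 SD the formula gives about 10% to 27% for same-day correlations of 0.7 to 0.9.
- A reader might extend the figures to the mediation model. That slope was not simulated, and change in KYNA is a post-dose, non-randomised predictor. Adding the pre-dose score there also changes what the slope is conditional on.

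Finally, the moderation model says only behavioural outcome. That it covers the six cognitive tests is a natural reading, not an explicit statement.

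**Conclusion.** The point holds as a minor loss of efficiency. For outcomes with a pre-dose score, the planned moderation model gives a wider standard error for treatment by KYNA than the collected data require, unless the within-person same-day correlation is very high. The excess is about 0% to 3% at a correlation of 0.9, roughly 10% to 15% at 0.5 and about 35% to 41% at 0. These figures assume about 45 completers per group, a small day effect and a comparator with a free within-person slope. Nearly all of the gain comes from the pre-dose score. Day contributes about 1% or less at the plan's d < 0.1. The documents show no bias and no excess false-positive rate from this choice.

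**What to change.** In the Secondary Aim 2 moderation model, use the post-dose score as outcome. Add the same-day pre-dose score as two covariates, the person's mean over the two days and each day's deviation from it, and add day for consistency with Aim 1. Keep the treatment, KYNA and interaction terms as planned. Change may be kept as the outcome if preferred: once both pre-dose covariates are in the model, the estimates for the other terms are the same. State the assumed or observed within-person correlation beside any precision figure.

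The same covariates can be added to the mediation model, with a note that change in KYNA is not randomised and that its slope is then conditional on the pre-dose score.

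The cost is a few lines of analysis-plan wording and two or three model degrees of freedom, using scores already scheduled. If the within-person correlation is very high, those degrees of freedom can cost slightly more than they return.
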